11 STATISTICAL CONSIDERATIONS

Three analyses are planned:

1. An interim analysis (IA) will be conducted approximately 2 months after 126 participants have been enrolled into the mITT population. A nominal 1-sided alpha of 0.0025 will be spent, but there will be no early study termination for efficacy.
2. The primary analysis (PA) will be conducted approximately 6 months after 126 participants have been enrolled into the mITT population, with 1-sided alpha 0.0225 (or 0.025 if the ORRs of both arms are significant at interim).
3. A follow-up analysis will be conducted approximately 12 months after 126 participants have been enrolled into the mITT population.

Additional analyses will be conducted to include adolescent participants and Companion Study participants, approximately 6 months after completion of enrollment of the respective participants.

Alpha will only be allocated to the primary endpoint, ORR.

11.1 HYPOTHESIS

This study is designed to show an ORR of at least 30% in participants with cGVHD, treated with belumosudil after at least 2 prior lines of systemic therapy.

11.2 SAMPLE SIZE AND POWER CALCULATION

Sample size is based on the primary efficacy endpoint of ORR, with one planned interim analysis (0.0025 1-sided alpha spending) and a target ORR of 55%. With 63 participants, and a 10% dropout rate, each treatment arm is estimated to have approximately 90% power to yield a 95% confidence interval of ORR that excludes 30% (equivalently, 90% power to reject the null hypothesis of ORR $\leq 30\%$ at 1-sided alpha level 0.0225).

The Hochberg procedure will be used for multiplicity adjustment for the primary endpoint of ORR as described below ([Section 11.2.1](#)).

[Table 5](#) provides powers for interim analysis ([Table 5a](#)) under various hypothetic ORRs to exclude 30%, and provides study powers under various hypothetic ORRs for at least one arm to exclude 30% at primary analysis ([Table 5b](#)).

Table 5 - Power for Various Hypothetic ORRs

		Table 5a: IA Power (1-sided alpha 0.0025)*				
		For both arms to be statistically significant				
		Arm 1 ORR (%)				
Arm 2 ORR (%)	40	40	45	50	55	60
	40	<1	<1	<1	<1	<1
	45	-	<1	1	2	3
	50	-	-	2	6	9
	55	-	-	-	12	22
	60	-	-	-	-	37
		For at least one arm to be statistically significant				
		Arm 1 ORR (%)				
Arm 2 ORR (%)	40	40	45	50	55	60
	40	1	3	10	28	51
	45	-	5	12	29	53
	50	-	-	20	35	57
	55	-	-	-	65	65
	60	-	-	-	-	77
		Table 5b: PA Power (1-sided alpha 0.0225)*				
		Arm 1 ORR (%)				
Arm 2 ORR (%)	40	40	45	50	55	60
	40	20	39	64	84	95
	45	-	52	72	89	97
	50	-	-	83	93	98
	55	-	-	-	97	99
	60	-	-	-	-	100

IA = Interim Analysis; PA = Primary Analysis

* Power estimated based upon 10,000 simulations for each cell

A 10% dropout rate (non-efficacy and non-safety related) is assumed based upon preliminary data from the ongoing KD025-208 study. If during the course of the current study the dropout rate is observed to exceed 10%, the sample size may be adjusted eg, to approximately 85 participants per arm if the dropout rate reaches 15%.

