11.2.1 Efficacy Decision Rules with Multiplicity Adjustment

The Hochberg procedure is the primary multiplicity adjustment method for inferential purposes for the primary endpoint ORR.

The inferential decision for primary endpoint of ORR is described below and shown in [Figure 2](#).

1. Calculate two-sided 99.5% confidence interval of ORR by using Clopper-Pearson (exact) method for both arms at interim analysis.
2. If the lower bounds of their 2-sided 99.5% confidence interval both are above 30%, then claim both arms are efficacious, and stop. Otherwise, go to Step 3.
3. If the lower bounds of their 2-sided 99.5% confidence interval both are below 30%, then cannot determine efficacy for either arm, and go to Step 5. Otherwise, go to Step 4.

[figure not shown]
4. Calculate 2-sided 99.75% confidence interval of ORR by using Clopper-Pearson (exact) method for treatment group with higher response rate. If its lower bound is above 30%, then claim this arm is efficacious, and go to step 6. Otherwise, cannot decide efficacy for both arms, and go to Step 5.
5. Use following Hochberg procedure for the 6-month primary efficacy analysis of ORR
 - a) Calculate 2-sided 95.5% confidence interval of ORR by using Clopper-Pearson (exact) method for both arms.
 - b) If the lower bounds of their 2-sided 95.5% confidence interval both are above 30%, then claim both arms are efficacious, and stop. Otherwise, go to Step 5c.
 - c) If the lower bounds of their 2-sided 95.5% confidence interval both are below 30%, then claim both arm are non-efficacious, and stop. Otherwise, go to Step 5d.
 - d) Calculate 2-sided 97.75% confidence interval of ORR by using Clopper-Pearson (exact) method for treatment group with higher response rate. If its lower bound is above 30%, then claim this arm is efficacious, and stop. Otherwise, claim both arms are non-efficacious, and stop.
6. At the 6-month primary analysis, calculate 2-sided 95.5% confidence interval (CI) of ORR by using Clopper-Pearson (exact) method for the treatment group with lower response rate at interim analysis. If its lower bound is above 30%, then claim this arm is efficacious, and stop. Otherwise, claim this arm is non-efficacious, and stop.

If one arm is discontinued in view of the prescribed stopping rules ([Section 10](#)), efficacy will only be assessed for the remaining arm without multiplicity adjustment.

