**Figure 2 ORR Multiplicity Adjustment**

Simulations were conducted with various hypothetical ORR scenarios for two arms of 63 subjects, by using the Hochberg procedure for multiplicity adjustment; results (10000 runs per setting) are presented in [Table 1](#).

Only descriptive statistics will be provided for all secondary and exploratory endpoints, without multiplicity adjustment.

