**Table 1: Power for various hypothetic ORRs**

Table 1a: IA Power (1-sided alpha 0.0025)*						
For both arms to be statistically significant						
		Arm 1 ORR (%)				
		40	45	50	55	60
Arm 2 ORR (%)	40	< 1	< 1	< 1	< 1	< 1
	45	-	< 1	1	2	3
	50	-	-	2	6	9
	55	-	-	-	12	22
	60	-	-	-	-	37
For at least one arm to be statistically significant						
		Arm 1 ORR (%)				
		40	45	50	55	60
Arm 2 ORR (%)	40	1	3	10	28	51
	45	-	5	12	29	53
	50	-	-	20	35	57
	55	-	-	-	65	65
	60	-	-	-	-	77
Table 1b: PA Power (1-sided alpha 0.0225)*						
		Arm 1 ORR (%)				
		40	45	50	55	60
Arm 2 ORR (%)	40	20	39	64	84	95
	45	-	52	72	89	97
	50	-	-	83	93	98
	55	-	-	-	97	99
	60	-	-	-	-	100

IA = Interim Analysis; PA = Primary Analysis  
\* Power estimated based upon 10,000 simulations for each cell

The mITT population will be used for tables of demography, baseline characteristics and efficacy.

**Responder:** The responder population is defined as subjects in the mITT population that achieved a partial or complete response at any post-baseline response assessment.

**Nonresponder:** The nonresponder population is defined as anyone in mITT population that is not a responder.

The responder and nonresponder populations will be used for some subgroup analyses.

**Safety:** The safety population is defined as all randomized subjects who receive at least one dose of study medication. In this study, safety population is equivalent to mITT population.

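### The interim power panel (Protocol Table 5a, SAP Table 1a) does not follow from the stated inputs: an unstated further discount of about 10% fits 29 of its 30 cells, and the 55/55 at-least-one cell is wrong with or without it

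*Protocol*

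**What the plan says.** Protocol 11.2 sets the planning basis: "With 63 participants, and a 10% dropout rate, each treatment arm is estimated to have approximately 90% power", for a target ORR of 55% and a null of 30%. SAP 3.2 says how the tables were produced: "Simulations were conducted with various hypothetical ORR scenarios for two arms of 63 subjects, by using the Hochberg procedure for multiplicity adjustment", with 10,000 runs per setting.

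The interim takes place once all 126 participants are in: "An interim analysis (IA) will be conducted approximately 2 months after 126 participants have been enrolled into the mITT population". The primary analysis follows at about 6 months after the same point.

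The interim decision rule is in Protocol 11.2.1. Step 1 is "Calculate two-sided 99.5% confidence interval of ORR by using Clopper-Pearson (exact) method for both arms at interim analysis"; if both lower bounds exceed 30%, both arms are claimed. If only one does, Step 4 applies: "Calculate 2-sided 99.75% confidence interval of ORR by using Clopper-Pearson (exact) method for treatment group with higher response rate".

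SAP 3.1 defines dropouts as participants who stop treatment before any response assessment, other than for a related adverse event or cGVHD progression. SAP 3.8.1 counts treated participants lost without an assessment as non-responders.

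The interim figures are in the Protocol panel "Table 5a: IA Power (1-sided alpha 0.0025" and, with identical numbers, in the SAP panel "Table 1a: IA Power (1-sided alpha 0.0025". Neither panel, nor its note, gives any interim assumption beyond these inputs.

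**The concern.** The interim and primary panels sit in one table, share column headings and are introduced by the same text, so a reader takes them to rest on the same inputs. The interim spends alpha and can lead to an efficacy claim for one or both arms, so its stated operating characteristics should be reproducible. If an unlabelled assumption lies behind the interim panel, its ORR columns do not mean the same thing as those in Table 5b. Anyone who uses them to judge how likely an interim claim was would then be misled by tens of points.

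**Working it through.** **Inputs.** n = 63 per arm and 10% dropout (Protocol 11.2, SAP 3.1); dropouts stay in the denominator as non-responders (SAP 3.8.1), so the response probability per participant is p = 0.90 × ORR; exact limits against 30% (Protocol 11.2.1). The arms are taken as independent.

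**Critical counts out of 63** (smallest count whose Clopper-Pearson lower limit exceeds 30%):
- Interim: 30 at 99.5% (lower limit 0.3005) and 31 at 99.75% (0.3027).
- Primary: 27 at 95.5% (0.3021) and 28 at 97.75% (0.3010).

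**Formulas.** For arm i, let A_i be the probability of reaching the lower of the two counts and H_i the probability of reaching the higher.
- Both arms = A_1 × A_2
- At least one = 1 − (1 − H_1)(1 − H_2) + (A_1 − H_1)(A_2 − H_2)

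**Step 1: the plan's primary-analysis figures.** At p = 0.90 × 0.55 = 0.495, single-arm power is P(X ≥ 27) = 88.1%, against the stated 90% or so. All 15 cells of Table 5b reproduce within 1 point (for example 40/40: 20.0 against 20; 50/50: 83.6 against 83; 55/55: 97.2 against 97). The stated inputs therefore explain that panel.

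**Step 2: the interim on the same basis.** At p = 0.495, A = 66.4% and H = 56.8%. At 55/55:
- Both arms = 0.664² = 44.1%, printed 12.
- At least one = 1 − 0.432² + 0.096² = 82.3% (unrounded inputs), printed 65.

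**Step 3: the interim at 0.81 × ORR.** At p = 0.81 × 0.55 = 0.4455, A = 35.7% and H = 26.8%. At 55/55:
- Both arms = 0.357² = 12.7%, printed 12.
- At least one = 47.2%, printed 65.

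**All 30 interim cells** (per cent, n = 63):

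| ORRs | Both: printed | 0.90 × ORR | 0.81 × ORR | At least one: printed | 0.90 × ORR | 0.81 × ORR |
|---|---|---|---|---|---|---|
| 40/40 | <1 | 0.1 | 0.0 | 1 | 4.3 | 0.8 |
| 40/45 | <1 | 0.6 | 0.0 | 3 | 12.1 | 3.0 |
| 40/50 | <1 | 1.5 | 0.1 | 10 | 30.9 | 10.5 |
| 40/55 | <1 | 2.6 | 0.3 | 28 | 57.9 | 27.1 |
| 40/60 | <1 | 3.4 | 0.5 | 51 | 81.8 | 51.4 |
| 45/45 | <1 | 2.3 | 0.2 | 5 | 19.5 | 5.1 |
| 45/50 | 1 | 5.9 | 0.7 | 12 | 36.9 | 12.5 |
| 45/55 | 2 | 10.2 | 1.6 | 29 | 61.7 | 28.8 |
| 45/60 | 3 | 13.4 | 2.8 | 53 | 83.5 | 52.6 |
| 50/50 | 2 | 14.8 | 2.3 | 20 | 50.7 | 19.5 |
| 50/55 | 6 | 25.5 | 5.5 | 35 | 70.3 | 34.7 |
| 50/60 | 9 | 33.5 | 9.4 | 57 | 87.3 | 56.6 |
| 55/55 | 12 | 44.1 | 12.7 | 65 | 82.3 | 47.2 |
| 55/60 | 22 | 58.0 | 21.8 | 65 | 92.5 | 65.1 |
| 60/60 | 37 | 76.3 | 37.3 | 77 | 96.9 | 77.1 |

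At 0.90 × ORR only two cells agree with print (both arms, 40/40 and 40/45). The largest gap is 76.3 − 37 = 39.3 points. At 0.81 × ORR, 29 of 30 cells agree within 0.9 points. Simulation error with 10,000 runs is at most √(0.25/10,000) = 0.5 points, so it cannot explain gaps of this size.

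**Step 4: the 55/55 at-least-one cell.** This check needs neither n nor the discount. With independent arms at equal ORR, a both-arms power of 12 to 12.5% implies A = √0.12 to √0.125, about 35%. At least one cannot then exceed 1 − (1 − A)² = 57% to 58%. The printed 65 conflicts with the 12 in the same table. It equals the neighbouring 55/60 entry, so a copying slip is possible.

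**Step 5: sensitivity at 55/55**, with 10% dropout and varying the share of eventual responses seen by the interim:

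| Share seen | Both arms | At least one |
|---|---|---|
| 100% | 44.1 | 82.3 |
| 95% | 26.2 | 66.4 |
| 90% | 12.7 | 47.2 |
| 85% | 4.9 | 28.9 |

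No share in this table gives both 12 and 65.

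**The case against.** The strongest reply is that the two panels ought to differ. The interim falls about 2 months after the 126th participant and the primary analysis about 6 months after. ORR counts a response at any post-baseline assessment, so the observed rate can only rise with follow-up, and SAP 3.8.2.4 tabulates time to response out to 48 weeks and beyond. A factor of 0.81 is 0.9 × 0.9, which can be 10% dropout times 90% of responses seen by the interim. On that reading 29 cells are right, and recomputing at 0.90 × ORR would overstate interim power.

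This stands as an explanation, but it does not make the table reproducible. The documents nowhere give the share of responses expected by the interim, and the result is very sensitive to it.

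A reader might infer that the dropout was counted twice, or that interim power is simply understated by up to 39 points. The documents support neither as fact. The 39 points hold only if all eventual responses are already in at the interim, which no section states. Nor is 0.81 the only fit: n = 56 with 0.85 × ORR matches the same 29 cells almost as well. That alternative departs from the stated 63, and it too misses the 55/55 at-least-one cell (about 47).

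The consequences are limited. The study does not stop early for efficacy, the sample size rests on single-arm power at the primary analysis, and the Protocol says approval was already granted on this study's data.

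**Conclusion.** The point holds as a reproducibility and reporting defect. From the stated inputs, 28 of the 30 interim cells cannot be obtained, with gaps of up to 39 points, while the same sample size and dropout reproduce Table 5b. At n = 63 the interim panel matches a further discount of about 10% on the response rate. Its origin is undetermined: double-counted dropout or an assumed 90% response maturity would give the same numbers. One cell, at least one arm at 55/55, is wrong whichever applies: 47 at 0.81 × ORR or 82 at 0.90 × ORR, against 65 printed in both documents.

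This rests on independent arms, dropouts counted as non-responders and the exact limits of Protocol 11.2.1. Sample size, Table 5b and the decision rules do not depend on the interim panel.

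**What to change.** In both Protocol Table 5a and SAP Table 1a, establish from the simulation program which response probability was used, then do one of the following.

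- **No maturity discount intended:** replace the whole interim panel with the 0.90 × ORR values tabulated above, rounded. This includes the both-arms 40/x row (<1, <1, 1, 3, 3) and 45/45 (2). The 55/55 at-least-one cell becomes 82.
- **Discount intended:** state the factor and its rationale in the table note, label the columns as final ORR, and show the both-arms sensitivity at 55/55 (about 44, 26, 13 and 5 with 100%, 95%, 90% and 85% of responses seen). If the factor is 90%, the other 29 cells stand and the 55/55 at-least-one cell becomes 47.

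The cost is one recalculation and a replacement table or note in each document. Design, conduct and decision rules do not change.

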11.2.1 Efficacy Decision Rules with Multiplicity Adjustment

The Hochberg procedure is the primary multiplicity adjustment method for inferential purposes for the primary endpoint ORR.

The inferential decision for primary endpoint of ORR is described below and shown in [Figure 2](#).

1. Calculate two-sided 99.5% confidence interval of ORR by using Clopper-Pearson (exact) method for both arms at interim analysis.
2. If the lower bounds of their 2-sided 99.5% confidence interval both are above 30%, then claim both arms are efficacious, and stop. Otherwise, go to Step 3.
3. If the lower bounds of their 2-sided 99.5% confidence interval both are below 30%, then cannot determine efficacy for either arm, and go to Step 5. Otherwise, go to Step 4.

[figure not shown]
4. Calculate 2-sided 99.75% confidence interval of ORR by using Clopper-Pearson (exact) method for treatment group with higher response rate. If its lower bound is above 30%, then claim this arm is efficacious, and go to step 6. Otherwise, cannot decide efficacy for both arms, and go to Step 5.
5. Use following Hochberg procedure for the 6-month primary efficacy analysis of ORR
 - a) Calculate 2-sided 95.5% confidence interval of ORR by using Clopper-Pearson (exact) method for both arms.
 - b) If the lower bounds of their 2-sided 95.5% confidence interval both are above 30%, then claim both arms are efficacious, and stop. Otherwise, go to Step 5c.
 - c) If the lower bounds of their 2-sided 95.5% confidence interval both are below 30%, then claim both arm are non-efficacious, and stop. Otherwise, go to Step 5d.
 - d) Calculate 2-sided 97.75% confidence interval of ORR by using Clopper-Pearson (exact) method for treatment group with higher response rate. If its lower bound is above 30%, then claim this arm is efficacious, and stop. Otherwise, claim both arms are non-efficacious, and stop.
6. At the 6-month primary analysis, calculate 2-sided 95.5% confidence interval (CI) of ORR by using Clopper-Pearson (exact) method for the treatment group with lower response rate at interim analysis. If its lower bound is above 30%, then claim this arm is efficacious, and stop. Otherwise, claim this arm is non-efficacious, and stop.

If one arm is discontinued in view of the prescribed stopping rules ([Section 10](#)), efficacy will only be assessed for the remaining arm without multiplicity adjustment.

The 12-month follow up analyses is an extension of the primary analysis with more mature data for DOR and other endpoints.

In addition to inferential analysis results, nominal 95% CIs will be provided for ORR and other efficacy endpoints without multiplicity adjustment.

Figure 2 - ORR Multiplicity Adjustment

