## **3.8 Efficacy Endpoints and Analyses**

### **3.8.1 Primary Efficacy Endpoint: ORR**

The primary efficacy endpoint is the overall response rate, with response status as assessed by investigators based upon the 2014 NIH Consensus Development Project on Clinical Trials in cGVHD (see Protocol Appendix F: cGVHD Response Assessment).

Response is assessed using individual scores from ten systems (Skin, Eyes, Mouth, Esophagus, Upper GI, Lower GI, Liver, Lungs, Joints and Fascia and Global Severity Rating (GSR)). Response is assessed with respect to the baseline (Cycle 1, Day 1 (C1D1)) cGVHD assessment. The overall response at each assessment time point will be categorized as Complete Response (CR), Partial Response (PR), or Lack of Response (LR), where LR includes the response status of unchanged, mixed, or progression as defined in [Table 2](#).

The ORR is defined as the proportion of subjects with a best response meeting the overall response criteria assessment of CR or PR at any post-baseline response assessment.

If a treated subject is lost to follow up without response assessment, this subject will be counted as a non-responder. Any response on and after new systemic cGVHD treatment will be censored as non-response.

Point estimates, various confidence intervals (Clopper-Pearson (exact) method) listed in Figure 2, and raw and Hochberg adjusted p-values corresponding to the null hypothesis of  $ORR \leq 30\%$  vs alternative hypothesis of  $ORR > 30\%$  by treatment arms will be reported.

The number and percentage of subjects who have a best response of PR and number and percentage of subjects who have a best response of CR will also be reported.

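### Protocol 11.2.1 turns a failure to exclude a 30% ORR into a positive claim that an arm is non-efficacious, which the test cannot support

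*Protocol*

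**What the plan says.** Protocol 11.2 sets a one-sided superiority test in each arm: "90% power to reject the null hypothesis of ORR $\leq 30\%$ at 1-sided alpha level 0.0225". SAP 3.8.1 states the same pair of hypotheses, ORR at or below 30% against ORR above 30%.

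Protocol 11.2.1 gives the decision steps. At the primary analysis:

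- **Step 5b:** both 95.5% lower bounds above 30%. Both arms are claimed efficacious.
- **Step 5c:** both 95.5% lower bounds below 30%: "then claim both arm are non-efficacious, and stop".
- **Step 5d:** one bound above and one below. The arm with the higher response rate is retested with a 97.75% interval. If its lower bound is not above 30%: "Otherwise, claim both arms are non-efficacious, and stop".
- **Step 6:** one arm has already succeeded at interim. The arm with the lower interim response rate is tested with a 95.5% interval, and if it fails: "Otherwise, claim this arm is non-efficacious, and stop".

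At the interim analysis, Steps 3 and 4 handle results that miss the bound differently. They say that efficacy cannot be determined, or decided, and pass to the primary analysis.

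**The concern.** A lower bound at or below 30% means that an ORR above 30% was not shown. It does not show that the ORR is 30% or less. A claim of that kind needs evidence from the other side, such as an upper bound below 30%, and 11.2.1 contains no such criterion. Reaching the last analysis explains why testing stops. It does not turn non-rejection into evidence for the null.

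Step 5d takes this further. An arm whose own 95.5% bound clears 30% is called non-efficacious because its 97.75% bound does not and the other arm fell short. Hochberg properly withholds rejection there, but withholding rejection is all it does.

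At stake is the pre-specified conclusion on the primary endpoint of a two-regimen trial. Followed to the letter, the rule could attach a negative efficacy statement to an active regimen because of limited precision or the multiplicity step alone.

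**Working it through.** **Inputs.** Protocol 11.2 gives the arm size and dropout rate: "With 63 participants, and a 10% dropout rate, each treatment arm is estimated to have approximately 90% power". The target ORR is 55% and the null is 30%. Intervals are Clopper-Pearson at 95.5% and 97.75% (11.2.1). SAP 3.8.1 gives the handling of dropouts: "If a treated subject is lost to follow up without response assessment, this subject will be counted as a non-responder".

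**Critical counts, n = 63.**

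| Responders | Rate | 95.5% interval | 97.75% lower bound |
|---|---|---|---|
| 11 | 17.5% | 8.9% to 29.4% | – |
| 12 | 19.0% | 10.1% to 31.2% | – |
| 26 | 41.3% | 28.8% to 54.7% | 27.3% |
| 27 | 42.9% | 30.2% to 56.2% | 28.7% |
| 28 | 44.4% | 31.7% to 57.8% | 30.1% |

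The 95.5% bound clears 30% from 27 responders and the 97.75% bound from 28. Anything from 12 to 26 responders gives a 95.5% interval that contains 30%, yet it can be labelled non-efficacious.

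**Step 5d example.** With 27/63 beside 26/63, one 95.5% bound is above 30% (30.2%) and one is below (28.8%). The 97.75% bound for 27/63 is 28.7%, so both arms are called non-efficacious. The same 27/63 beside another 27/63 makes both arms efficacious under Step 5b.

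**How often both arms are labelled.** Let X be binomial (63, p) in each arm, with q = P(X ≤ 26) and e = P(X = 27). Then

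- P(Step 5c label) = q²
- P(Step 5d label) = 2 × e × q
- P(both labelled) = q² + 2eq, which is 1 minus the power for at least one arm.

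Counting 10% dropouts as non-responders gives p = 0.9 × ORR:

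| ORR before dropout, both arms | p | q | e | 5c: q² | 5d: 2eq | Both labelled | 1 minus this | Table 5b |
|---|---|---|---|---|---|---|---|---|
| 40% | 0.360 | 0.8420 | 0.0540 | 70.9% | 9.1% | 80.0% | 20.0% | 20 |
| 45% | 0.405 | 0.6026 | 0.0941 | 36.3% | 11.3% | 47.7% | 52.3% | 52 |
| 50% | 0.450 | 0.3211 | 0.0954 | 10.3% | 6.1% | 16.4% | 83.6% | 83 |
| 55% | 0.495 | 0.1187 | 0.0579 | 1.4% | 1.4% | 2.8% | 97.2% | 97 |

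The last two columns agree to within a point, so this convention reproduces Table 5b. Single-arm power at 55% is 1 − 0.1187 = 88.1%, against about 90% stated. The alternatives do not reproduce the table: at 45%/45%, 57 evaluable per arm gives 77.5% and no dropout gives 83.6%, against the printed 52%.

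**Other reading of 45%.** Protocol 11.7.1 defines ORR as a proportion of the mITT population. If 45% is that proportion, then p = 0.45 and both arms are labelled in 16.4% of trials.

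The table treats the primary analysis on its own. In a simulation with an assumed interim response probability of 0.78 to 0.82 times the ORR, which roughly brackets most of Table 5a, the both-arms figure at 45%/45% stays near 48%. Step 6 then adds 1.8 to 3.7 points for a single labelled arm.

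**The case against.** The strongest reply is that this is a matter of wording with little practical effect.

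- **The interval is reported anyway.** SAP 3.8.1 requires point estimates, exact intervals, and raw and adjusted p-values. Protocol 11.2.1 adds nominal 95% intervals. A reader would see 26/63 with its interval. This stands and lowers the severity, but the prescribed claim would still sit beside an interval that contradicts it.
- **Nothing operational hangs on the label.** The documents do not tie it to dropping an arm, and the 12-month analysis follows regardless. This stands.
- **The rule has probably been used already.** The Protocol synopsis says approval rested on data from this study, and section 1.6 dates it to July 2021. The documents do not say which analysis supported it, and the wording remains in the current amendment.
- **The frequencies are ordinary type II error.** This is correct. They show how often the wrong conclusion would be written, and rewording does not change them.

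Three stronger readings are tempting but unsupported. First, a reader might infer that nearly half of trials with a 45% mITT ORR end in a false claim. The 48% belongs to 45% before dropout, that is 40.5% in the mITT population. Second, a reader might apply the single-arm probability of 26 or fewer responders (60% at 45%, 32% at 50%, both before dropout) to Step 6. That step is reached only after the other arm has succeeded at interim, and it concerns the arm with the lower interim rate, so an unconditional probability does not describe it. Third, a reader might infer a fault in error control. The Hochberg steps are sound for claims of efficacy.

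**Conclusion.** The point holds as a fault in the prescribed conclusion. Steps 5c, 5d and 6 assert non-efficacy on the strength of non-rejection alone, against the logic of the test and of interim Steps 3 and 4.

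Its size depends on the true rate and on what that rate means. Both arms would be labelled in about 48% of trials at 45%/45% before dropout (36% through Step 5c, 11% through Step 5d), about 16% if 45% is the mITT ORR, and about 3% at the 55%/55% target. These figures assume 63 per arm, independent arms and, except for the 16%, 10% dropouts counted as non-responders.

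Severity is minor to moderate, because the estimates and intervals are reported and no trial action follows from the label. Whether the SAP repeats the wording cannot be judged: its readable text does not use it, and Figure 2 is not shown.

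**What to change.** In Protocol 11.2.1 Steps 5c, 5d and 6, replace the claim of non-efficacy with a statement that efficacy (ORR above 30%) was not demonstrated, in line with Steps 3 and 4. Report it with the ORR and the exact interval that the SAP already requires. Make the same change in Figure 2 of both documents if it carries the wording.

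If the sponsor wants to be able to state lack of efficacy, it could add a criterion such as an upper limit below 30% (11/63 or fewer at the 95.5% level). That is optional.

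The cost is a wording change. Critical values, alpha, power and sample size stay as they are.
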